1 SYNOPSIS

TITLE	Retrospective post-market Clinical Investigation for the evaluation of the safety and clinical benefit of Guided Growth Plate System Plus (Orthofix Srl) medical device for the treatment of lower limb bone deformities of the in growing children.
INVESTIGATIONAL DEVICE DESCRIPTION	The GGPSP consists of different sizes of eight-Plate and quad-Plate designed to accept cannulated or solid screws available in a variety of sizes. Plates and screws are available in sterile or non-sterile configuration. The device is designed for the gradual correction of pediatric congenital as well as acquired bone deformities in long bones, provided that the physis (growth plates) are not fused. The plates feature a contoured waist and low profile for pediatric usage. There is a center hole in the plates for a temporary guide pin to be implanted to aid application and removal of the plate. The plates are fixed to the bone over the growth plate by screws. These screws are not locked to the plate, but rather are allowed to swivel and diverge in their position as bone growth occurs. The implant acts like a flexible hinge, halting on one side (hemiepiphysiodesis) or on both sides (epiphysiodesis) the growth plate and thus guiding bone growth. Application and removal of the GGPSP can be performed with Orthofix general orthopaedic instrumentation.
OBJECTIVES AND ENDPOINTS	
Primary objective: evaluate the safety profile of GGPSP.
 
Primary endpoint: percentage of subjects that encountered at least one complication, to be intended as:
 
 · an expected or unexpected serious adverse effect related to the device; · an hardware failure (i.e. breaking, loosening or bending of the plate or of the screws) during follow-up period (from time of plate application to the first post-removal visit). 
Secondary objective: evaluate the clinical benefit of treatment with the GGPSP.
 
Secondary endpoint: percentage of subjects that achieved the treatment goal as defined below:
 
 · for hemiepiphysiodesis, femur and/or tibia angular deformity partially or completely corrected to standard alignment (mMPTA and mLDA between 85° and 89°); · for epiphysiodesis, femur and/or tibia length discrepancy partially or completely corrected to the matching length of the contralateral morphologically normal limb during follow-up period (from time of plate application to the first post-removal visit).

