8.4 Endpoints

In this Clinical Investigation, the two variables selected as the primary and secondary endpoints, intended to measure the primary and secondary objectives of the Investigation respectively, also correspond to the treatment response measures routinely used in the standard clinical practice of the participating Centre, namely:

- **Primary endpoint (safety measure):**

The safety of the 8-Plate Plus will be assessed by the percentage of subjects who, during the observation period — i.e., from plate implantation to the first follow-up visit after plate removal — experienced at least one complication certainly or potentially related to the investigational device. Such complications are defined as:

- a Serious Adverse Device Effect (SADE), expected or unexpected;
- a hardware failure (e.g., breakage, detachment, or bending of the plate or screws).

- **Secondary endpoint (benefit measure):**

The clinical benefit of treatment with the 8-Plate Plus will be assessed by the percentage of subjects who, during the observation period — i.e., from plate implantation to the first follow-up visit after plate removal — achieved the treatment objective, defined as:

- for hemiepiphysiodesis: partial or complete correction of the angular deformity of the femur and/or tibia towards the standard alignment direction (mMPTA and mL DFA between 85° and 89°);
- for epiphysiodesis: partial or complete correction of femoral and/or tibial length discrepancy in relation to the morphologically normal contralateral limb length.

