8.5 Methods of Endpoint Assessment

The **primary endpoint (safety measure)** of this Clinical Investigation will be assessed as follows:

- The correlation of a serious adverse event with the 8-Plate Plus will be freely determined by the Investigator according to the following options: not related / possibly related / definitely related. Serious events assessed as possibly or definitely related to the 8-Plate Plus will be included in the safety measure calculation.
- It is understood that, for serious events judged as possibly or definitely related to the 8-Plate Plus, the Sponsor reserves the right to supplement the Investigator's assessment with the opinion of an independent orthopaedic surgeon. If the independent orthopaedic surgeon subsequently identifies a surgical technique error in the primary implantation, in agreement with the Investigator, the event initially classified as possibly or definitely related to the 8-Plate Plus may be reclassified as not related and, consequently, excluded from the safety measure calculation. Similarly, serious adverse events due to use not compliant with the manufacturer's Instructions for Use (off-label use) will be excluded from the safety measure calculation.

The **secondary endpoints (benefit measures)** of this Clinical Investigation, as described above, will be assessed by comparing, for each patient, the preoperative radiographs (untreated deformity) with the radiographs collected at the plate removal visit (Visit 4).

The data related to the primary and secondary endpoints, already available in the patients' medical records, will be:

- entered into the validated electronic database provided free of charge by the Sponsor to each Investigator for data collection within the Clinical Investigation;
- analysed using descriptive and/or quantitative statistics and presented with the corresponding confidence intervals (for further details, see the *Statistics* section of this Clinical Investigation Plan).

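### Sections 8.4 and 8.5 leave open whether a hardware failure that is also a serious event stays in the primary endpoint; read literally, it can be excluded while a non-serious failure with the same cause counts

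*Combined protocol and SAP*

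**What the plan says.** Section 8.4 defines the primary endpoint, which it calls the safety measure, as the percentage of subjects who "experienced at least one complication certainly or potentially related to the investigational device. Such complications are defined as" either of two items. The first is "a Serious Adverse Device Effect (SADE), expected or unexpected". The second is "a hardware failure (e.g., breakage, detachment, or bending of the plate or screws". The second item has no seriousness condition.

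The synopsis has the same two-part structure. Its second bullet reads "an hardware failure (i.e. breaking, loosening or bending of the plate or of the screws) during follow-up period". There, the requirement of a relation to the device appears only in the serious-effect bullet.

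Section 8.5 explains how the safety measure is assessed, but all its rules concern serious events:

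- Inclusion: "Serious events assessed as possibly or definitely related to the 8-Plate Plus will be included in the safety measure calculation".
- Exclusion for technique error: the sponsor may obtain the opinion of an independent surgeon. If that surgeon finds an error in the primary implantation and the investigator agrees, the event "may be reclassified as not related and, consequently, excluded from the safety measure calculation".
- Exclusion for off-label use: "serious adverse events due to use not compliant with the manufacturer's Instructions for Use (off-label use) will be excluded from the safety measure calculation".

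Section 15 makes re-hospitalisation a seriousness criterion. Section 8.6.1 admits only patients treated according to the Instructions for Use.

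**The concern.** Some hardware failures are also serious events, for example a broken screw that leads to re-hospitalisation. Such an event falls under both sets of rules. By the second item of 8.4 it is a complication. By 8.5 it may be taken out of the safety measure altogether once it is attributed to technique error. A breakage with the same cause but no serious consequence is never reached by the 8.5 rules, so it stays in by default.

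Two things are at stake. First, the asymmetry runs the wrong way for a device safety claim, because the only hardware failures with a way out are the serious ones. Second, the review in 8.5 applies only to events already judged possibly or definitely related, so it can lower the rate and never raise it. The events are already in the medical records, so an unwritten rule would be settled with the events in view.

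**Working it through.** **Step 1. The rules side by side.** Take hardware failures attributed to an error in the primary implantation.

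| Hardware failure | Section 8.4, second item | Section 8.5 |
|---|---|---|
| Not serious | Listed as a complication | No rule; no exclusion route |
| Serious (e.g. re-hospitalisation) | Listed as a complication | May be excluded from the whole safety measure |

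No section says whether a failure excluded in the second row still counts under the second item of 8.4. This gap does not depend on the small difference between the failure types named in 8.4 and in the synopsis.

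**Step 2. Reproduce the plan's figure.** Inputs from sections 8.7 and 16: expected rate 3%, 70 implants, about 40 patients, exact binomial 95% interval, upper limit to be below 12% (stated as 9.94%). For x events in n units, the two-sided exact upper limit is the 0.975 quantile of Beta(x + 1, n − x).

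- Expected events: 0.03 × 70 = 2.1, taken as 2.
- x = 2, n = 70: the 0.975 quantile of Beta(3, 68) is 9.94%. The stated figure is reproduced.

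**Step 3. Effect of one event counted or dropped.** The sample size is given in implants and the endpoint in subjects, so both denominators are shown. For 40 patients the expected number is 0.03 × 40 = 1.2.

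| Units | Event counted | Event dropped | Difference in upper limit |
|---|---|---|---|
| 70 | 3/70 = 4.3%, upper 12.02% | 2/70 = 2.9%, upper 9.94% | 12.02 − 9.94 = 2.08 points |
| 70 | 2/70 = 2.9%, upper 9.94% | 1/70 = 1.4%, upper 7.70% | 9.94 − 7.70 = 2.24 points |
| 40 | 1/40 = 2.5%, upper 13.16% | 0/40 = 0%, upper 8.81% | 13.16 − 8.81 = 4.35 points |
| 40 | 2/40 = 5.0%, upper 16.92% | 1/40 = 2.5%, upper 13.16% | 16.92 − 13.16 = 3.76 points |

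The first and third rows move the limit across 12%; the second and fourth do not. With subjects as the unit, dropping an event changes the count only if the subject has no other qualifying complication.

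**The case against.** A reader might infer that 8.4 counts every hardware failure whatever its cause, so that 8.4 and 8.5 flatly contradict each other. The documents do not go that far:

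- **Relatedness.** The lead-in of 8.4 requires a certain or potential relation to the device before listing both items, and section 8.7 repeats the qualifier. If it governs hardware failure too, a failure judged unrelated is outside the endpoint under 8.4 as well. Against this, 8.4 goes on to define such complications as including hardware failure, and the synopsis puts no such condition on that bullet. The text is ambiguous. Even on the narrower reading, 8.5 gives no procedure for judging a non-serious failure, so the asymmetry remains.
- **Scope of 8.5.** Its rules could be read as deciding only whether an event is a serious device effect, leaving the breakage counted under the second item. That is a sensible reading, but the wording excludes the event from the measure as a whole, and nothing states the narrower intent.
- **Off-label route.** This is largely closed by the inclusion criterion on the Instructions for Use. It is not quite empty, because section 8.15 says that data from discontinued and replaced patients are also analysed.
- **Technique-error route.** It needs the sponsor to seek review, the independent surgeon to find an error and the investigator to agree; even then reclassification is optional. Exclusion is possible, not automatic.
- **Numbers.** The crossings of 12% occur at particular counts, and 3 of 70 exceeds 12% by only 0.02 points. Any disputed event would have a similar effect in so small a sample.

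These points limit how strongly the concern can be put. They do not supply the missing rule.

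**Conclusion.** The gap is real and narrow. Sections 8.4 and 8.5 do not fit together for a hardware failure that is also serious. Followed literally, 8.5 can remove it through the technique-error route while a non-serious failure with the same cause counts. Any effect on the reported rate is downward.

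One such event moves the exact 95% upper limit by about 2 points with 70 units and about 4 points with 40 patients at the counts shown. At 3 versus 2 of 70, or 1 versus 0 of 40, it decides whether the limit is below 12%. These counts are close to the 2.1 and 1.2 events expected at the assumed 3%. The documents do not give the share of hardware failures that are serious, so the chance of this happening cannot be stated.

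A reader might also infer that crossing 12% would make the study fail. Section 16 plans descriptive reporting with a confidence interval; 12% serves as the sample-size target and the top of the literature range, and no pass or fail rule is attached to it. The matter should still be settled before events are classified, because it concerns the definition of the primary endpoint.

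**What to change.** - **Section 8.5:** state that both exclusions apply to the serious-effect component only. A hardware failure within the scope of 8.4 is counted under its own component, by the same rule whether or not it was serious.
- **Section 8.4 and synopsis:** align the relatedness wording with this, so that one text does not impose a condition on hardware failure that the other omits. If relatedness is to apply to hardware failure, 8.5 must say how it is judged, identically for serious and non-serious failures. Changing 8.5 alone, so that failures count whatever their attributed cause, would create a new conflict with the lead-in of 8.4.
- **Section 16:** report the number of subjects counted by serious device effect only, hardware failure only, and both. Give the primary percentage and its confidence interval with and without any event excluded under 8.5.

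The cost is a few sentences and one extra table line, with no new data. The downside is that the reported complication rate may be slightly higher.

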8.6.1 Inclusion criteria

A patient will be considered eligible for participation if:

- he/she has been diagnosed with an angular deformity or a femoral and/or tibial length discrepancy;

- at the time of treatment, he/she was younger than 18 years of age;
- at the time of treatment, the growth plates of the treated limb(s) were not yet closed;
- in the opinion of the Investigator, the angular deformity and/or length discrepancy represented a valid indication for surgical treatment with tension band plates;
- the deformity was treated with the 8-Plate Plus, in accordance with the manufacturer's Instructions for Use;
- the treatment with the 8-Plate Plus was completed and the patient underwent at least one follow-up visit after plate removal;
- the clinical data of the patient required for the evaluation of the device's safety and clinical benefit are still available.

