8.9 Clinical Investigation Duration

Given the retrospective nature of the Clinical Investigation and considering that the consent of eligible patients had already been obtained a priori, no study-specific procedures will be required of the patient. The duration of the study therefore foresees 2 months for patient screening and 4 months for retrospective data collection.

It is understood that the Sponsor, after database lock, unless otherwise agreed with the Investigators and/or the Ethics Committees, reserves a period of 4 months for end-of-study activities, namely:

- database review;
- opening and resolution of potential queries to the Investigators;
- drafting of the statistical report;
- drafting of the clinical report;
- site close-out visits;
- end-of-study notifications to the relevant Ethics Committees and Competent Authority.

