8.12 Table of procedures

PHASE		ENROLLMENT	TREATMENT				FOLLOW UP
VISIT	Number	Visit 0	Visit 1	Visit 2	Visit 3	Visit 4	Visit 5
	Type	Selection	Implant	1° Follow up	2° Follow up	Removal	Follow up post removal
Selection Criteria Verification		x	x	x	x	x	x
Demographics		x					
Medical History		x					
X-rays		x				x	
Technical Characteristics of the Device			x				
Device Implantation			x				
Safety Measures			x	x	x	x	x
Benefit Measures		x				x	

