8.14 Discontinuation and Withdrawal of Subjects from the Clinical Investigation

A patient will be considered prematurely discontinued from the study if, during the collection of data related to the visits following screening, the Investigator becomes aware that one of the inclusion or exclusion criteria is no longer fulfilled.

Patients prematurely discontinued will be recorded in the case report form through the dedicated discontinuation visit. The Investigator will be required to notify the Sponsor of all prematurely discontinued patients and, if the patient is not evaluable, i.e., discontinued before plate removal, may agree with the Sponsor on the replacement of the patient according to the procedure described below.

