- revise the Clinical Investigation Plan and any study documentation impacted by the amendments, ensuring that all changes are appropriately tracked;
- in the case of non-substantial amendments, promptly notify in writing the participating Site and the corresponding Ethics Committee for information purposes, providing copies of the revised documents;
- in the case of substantial amendments, suspend the Clinical Investigation until a new favourable opinion has been issued by the relevant Ethics Committee.

15 Adverse events

The foreseeable adverse events related to the use of the 8-Plate Plus, as identified through the risk analysis performed during product design, are described in the section “POSSIBLE ADVERSE EFFECTS” of the device’s Instructions for Use (http://abs.orthofix.it/db/resources/PQ_EPP.pdf).

This Clinical Investigation is a retrospective observational study and, therefore, does not pose additional risks to patients or Investigators.

Definitions:

- An *adverse event (AE)* is any undesirable experience associated with the use of the device in a patient.
- An *adverse event* is defined as a *serious adverse event (SAE)* when, as a consequence of such event, the patient:
 - dies;
 - experiences a life-threatening event;
 - requires prolongation of hospitalisation;
 - requires re-hospitalisation;
 - suffers permanent disability;
 - experiences a congenital anomaly or birth defect.

Expected Serious Adverse Device Effects (SADEs) — i.e., those already reported in the device Instructions for Use — are further classified as **E(SADE)** (*Expected SADE*). Conversely, Serious Adverse Device Effects not previously reported in the device Instructions for Use are further classified as **U(SADE)** (*Unexpected SADE*).

All adverse events and adverse device effects associated with the use of the device that occurred during the entire observation period of the Clinical Investigation will be classified and reported to the Sponsor via the electronic database provided by the Sponsor.

Since this is a retrospective Clinical Investigation, serious adverse events (SAEs), having already followed the reporting procedures of the vigilance system, are not subject to prompt notification upon awareness, as otherwise required by GCP (Section 4.11.1).

16 Statistics

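### Section 8.5 takes serious events ruled off-label out of the primary safety rate, with no deadline, no clear decision-maker and no planned analysis or listing that shows them

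*Combined protocol and SAP*

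**What the plan says.** The primary endpoint in 8.4 is the percentage of subjects with at least one complication certainly or potentially related to the device. It has two limbs: a serious adverse device effect, and "a hardware failure (e.g., breakage, detachment, or bending of the plate or screws").

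Section 8.5 lets the Investigator rate each serious event as not, possibly or definitely related, and counts the last two. It then gives two ways for an event to leave the count.

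- **Surgical technique error.** An independent surgeon, whom the Sponsor may choose to consult, can identify such an error. With the Investigator's agreement, the event may then be reclassified as not related.
- **Off-label use.** The next sentence begins "Similarly, serious adverse events due to use not compliant with the manufacturer" and ends "off-label use) will be excluded from the safety measure calculation". This exclusion is mandatory. It names no decision-maker and no time.

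Other sections bear on the rule:

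- **8.6.1** admits a patient only if "the deformity was treated with the 8-Plate Plus, in accordance with the manufacturer"'s Instructions for Use.
- **8.12** marks "Selection Criteria Verification" at every visit from 0 to 5.
- **8.14** treats a patient as prematurely discontinued if, while data are being collected after screening, "the Investigator becomes aware that one of the inclusion or exclusion criteria is no longer fulfilled".
- **8.9** lists, among the activities after database lock, "opening and resolution of potential queries to the Investigators".
- **15** has the following classified and reported in the database: "All adverse events and adverse device effects associated with the use of the device that occurred during the entire observation period".
- **16** plans one percentage with a 95% confidence interval for the primary endpoint. It defines no analysis set.

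**The concern.** The exclusion works in one direction. It can take an event out of the numerator and can never put one in. Because 8.6.1 screens for compliant use, any event it removes belongs to a patient whom the Investigator had already accepted as compliant. A judgement made at entry is then revisited because a serious event occurred. The text does not state that the ruling is made with the event known. That follows from a rule that acts on events in completed charts.

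Three things that would limit the discretion are missing or unclear: who rules, by when, and what happens to the patient. The final report is to compare the complication percentage and its interval with published safety data. With so few events expected, one ruling can change how that comparison looks, and no planned output would show that a ruling had been made.

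**Working it through.** **Inputs.** From 8.7 and 16: expected rate 3%, 70 implants in about 40 patients, exact binomial 95% interval, and a literature range of 3% to 12%. Both bases are shown, because the endpoint is per subject while the sample size is stated in implants.

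**The plan's own figure.** 3% of 70 is 2.1, taken as 2 events. The two-sided Clopper-Pearson upper limit is the 0.975 quantile of Beta(x + 1, n − x). For 2/70 this is 9.94%, as the plan states.

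**Effect of one removed event, patient kept in the denominator.**

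| Basis | Event counted | Event removed |
|---|---|---|
| 40 patients | 1/40 = 2.5%, upper limit 13.16% | 0/40 = 0%, upper limit 8.81% |
| 70 implants | 3/70 = 4.29%, upper limit 12.02% | 2/70 = 2.86%, upper limit 9.94% |

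On both bases the limit passes from above 12% to below it. On the implant basis the starting value is above 12% by only 0.02 points.

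**Does the denominator matter?** If the patient is dropped as well, 0/39 gives 1 − 0.025^(1/39) = 9.03%, against 8.81% for 0/40. The loss of the event drives the result.

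**How often could this happen?** The plan gives no figure. As an illustration only, let q be the share of patients with a complication whose only qualifying events are ruled off-label. With 40 patients the limit is below 12% only when no event is counted. The chance that rulings bring it from above to below 12% is therefore the chance of at least one patient with a complication and none left after removal:

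(1 − p(1 − q))^40 − (1 − p)^40, with p = 0.03 and 0.97^40 = 0.2957.

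- q = 0.02: 0.9706^40 − 0.2957 = 0.3031 − 0.2957 = 0.7%
- q = 0.05: 0.9715^40 − 0.2957 = 0.3146 − 0.2957 = 1.9%
- q = 0.10: 0.9730^40 − 0.2957 = 0.3346 − 0.2957 = 3.9%

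**Do other sections close the gap?**

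- *Deadline.* 8.15 uses database lock as a limit for replacing patients, not for classifying events. 8.9 places database review and queries after lock.
- *Late-found non-compliance.* 8.14 would discontinue the patient and 8.5 would remove the event. The plan does not say which applies, or whether both do.
- *Denominator.* Neither 8.5 nor 16 says whether the patient stays in.
- *Visibility.* 15 keeps the event on record. Section 16 contains no analysis that counts it and no listing.

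**The case against.** The strongest reply is that the rule should rarely be reached. Section 8.6.1 requires compliant use, 8.6.2 excludes patients with contraindications under the Instructions for Use, and 8.14 gives a route for a breach found later. Excluding off-label events is also a defensible target, because section 4 ties the risk/benefit judgement to use as the manufacturer intends. All of this stands. It is why the Sponsor can keep its 8.5 version, and why the illustrative probabilities are small.

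The decision-maker may be less open than it looks. The off-label sentence follows the surgeon-and-Investigator route and is linked to it by its opening word. That reading is possible, but the text does not settle it, and consulting the surgeon is optional.

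A reader might infer that removed events disappear. They do not. Complications are collected whether or not they are device-related (8.10), endpoint and adverse event data are to be monitored (section 9), the data system keeps an audit history (11), deviations are reviewed (13) and all adverse events are entered (15). What is missing is a planned output that shows them.

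A reader might also infer that hardware failures can be removed in the same way. They are a separate limb of the endpoint, and the exclusion does not name them.

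Another tempting inference is that patients with length discrepancy are off-label, since 2.2 speaks of angular deformities. The list in 2.2 is not closed, 2.3 presents epiphysiodesis as an intended use, and the Instructions for Use are not among the documents. Likewise, nothing shows whether the 3% to 12% range was computed with or without such an exclusion. Neither inference is relied on here.

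Finally, much of the fragility at 40 patients exists without the rule: the chance of at least one event at 3% is 1 − 0.2957 = 70.4%, and any event puts the limit above 12%. That comes from the small sample and the mix of patients and implants, which is a separate matter.

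**Conclusion.** The point holds as a gap in how the primary result is protected and shown. Section 8.5 orders the removal of certain serious events in patients already accepted as compliant, without a deadline, a clear decision-maker, a stated denominator or a planned analysis that counts them. If the patient stays in the denominator, the rule can lower the reported rate and cannot raise it. One removal is enough to move the exact upper limit across 12%: from 13.16% to 8.81% with 40 patients, or from 12.02% to 9.94% with 70 implants.

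The size of a single removal is certain arithmetic; its frequency is unknown. At a 3% rate and 40 patients, assumed shares of 2%, 5% and 10% give a chance of 0.7%, 1.9% and 3.9% that the limit crosses. The documents give no basis for any particular share, or for a larger one.

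A reader might conclude that the study could pass or fail on such a ruling. The documents do not support that: 12% is a planning and comparison reference, and section 16 sets no formal test. Nor do they show any intent to suppress events. The change is worth making before data are extracted, because it is cheap and leaves the Sponsor's own analysis in place.

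**What to change.** 1. **8.5 and 16 (the main safeguard).** Report the primary percentage and exact 95% confidence interval in all enrolled patients, counting every serious event the Investigator rated possibly or definitely device-related and every hardware failure. Place it next to the 8.5 version with exclusions. State the denominator of each, and list each excluded event with its reason. Hardware failures stay counted in both.
2. **8.5 and 8.9.** Name who makes the off-label ruling and require it before database lock. State in 8.9 that queries opened later cannot change it.
3. **8.5, 8.6.1 and 8.14.** Reconcile these on what follows when non-compliant use is found after enrolment: discontinuation, event removal or both, and whether the patient stays in the denominator.

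**Cost.** Wording in these sections, one additional percentage with its interval, and one listing. No new patient data are needed, since section 15 already brings all adverse events and device effects into the database. The downside for the Sponsor is that the rate with all events counted may be less favourable.
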